# 7.8 Study Product Discontinuation/Early Termination Visit

Study product discontinuation and early termination evaluations will be performed as described below. Women who must discontinue taking the study product, for reasons described in section 5.3.3.1, before the end of the study-defined treatment period, will be asked to stay in the study to be followed on study/off treatment until study completion. Women who terminate their participation in the study early will be asked to have one final study visit but could return to be followed on study/off treatment until study completion if circumstances of the termination change.

- 1. Staff will review symptoms, concomitant medications and any medical problems since the last visit, which will be recorded on the appropriate CRF. The participant will be asked to provide exact dates and times of the study product administration
- 2. Medical, gynaecological and sexual history to include assessment of STI risk
- 3. Symptom-directed physical and pelvic examination by a study physician or nurse that will include vital signs, including temperature, and examination of respiratory and cardiovascular systems, as well as assessment of symptoms and adverse events
- 4. The pelvic examination will be conducted in the following order:
  - a. Examination of the external genitalia
  - *b.* Speculum insertion and examination of vagina, fornices and cervix with naked eye. Water will be used to ease speculum insertion. No lubricant should be used as it could contain chlorhexidine which may kill *Lactobacillus.*
  - c. Vaginal pH
  - d. Vaginal swab for Gram stain (Nugent scoring system)
  - e. Two Vaginal swabs for complete mucosal sampling including identification of vaginal bacteria, lactobacilli species, cytokines and HIV target cells as well as multiomic (e.g. proteomics, metabolomics, etc.) testing
  - f. Vaginal swab for prostate specific antigen testing as a proxy for recent exposure to semen
  - g. Vaginal swab for STI testing if indicated by symptoms
  - h. A cervicovaginal lavage sample
  - i. Vaginal swabs for *L. crispatus* identification with qPCR
  - j. Vaginal swab for prostate specific antigen testing as a proxy for recent exposure to semen
- 5. Dipstick on clean catch urine; if abnormal, urinalysis (UA) will be performed.

- 6. Rapid Urine  $\beta$ hCG pregnancy test
- 7. All clinical and laboratory findings at the time of the evaluation will be recorded on the CRF. These findings will include observations present on the pelvic exam such as genital findings including location; presence or absence, and character of vaginal or cervical discharge or lesions; and results of any on site tests.
- 8. Administer acceptability questionnaire
- 9. If participants remain in follow up, they will receive non-spermicidal lubricated condoms for their male sexual partners. Participants will be encouraged to use condoms if they engage in vaginal intercourse throughout the study.
- 10. If the clinician suspects the participant developed an STI since the last visit, appropriate tests will be conducted and if needed the woman will be referred to standard of care treatment in compliance with current CDC STI Treatment Guidelines.

# 7.9 Unscheduled Visit

An unscheduled visit following a participant's request or the site investigator's recommendation should be recorded on the appropriate CRF. The following procedures and assessments may be performed at the unscheduled visit:

- 1. Staff will review symptoms, concomitant medications and any medical problems since the last visit, which will be recorded on the appropriate CRF. Additionally, the participant will be asked to provide exact dates and times of the study product administration.
- 2. Medical, gynaecological and sexual history to include assessment of STI risk
- 3. Symptom-directed physical and pelvic examination by a study physician or nurse that will include vital signs, including temperature, and examination of respiratory and cardiovascular systems, as well as assessment of symptoms and adverse events
- 4. The pelvic examination will be conducted in the following order:
  - a. Examination of the external genitalia
  - *b.* Speculum insertion and examination of vagina, fornices and cervix with naked eye. Water will be used to ease speculum insertion. No lubricant should be used as it could contain chlorhexidine which may kill *Lactobacillus.*
  - c. Vaginal pH
  - d. Vaginal swab for Gram stain (Nugent scoring system)
  - e. Two Vaginal swabs for complete mucosal sampling including identification of vaginal bacteria, lactobacilli species, cytokines and HIV target cells as well as multiomic (e.g. proteomics, metabolomics, etc.) testing
  - f. Vaginal swab for prostate specific antigen testing as a proxy for recent exposure to semen
  - g. Vaginal swab for STI testing if indicated by symptoms
  - h. Cervical (or vaginal) swabs for nucleic acid amplification of N. gonorrhoeae, and C. trachomatis.
  - i. A cervico-vaginal lavage sample
  - j. Vaginal swabs for *L. crispatus* identification with qPCR

- 5. Dipstick on clean catch urine; if abnormal, urinalysis (UA) will be performed.
- 6. Rapid Urine βhCG pregnancy test
- 7. All clinical and laboratory findings at the time of the evaluation will be recorded on the CRF. These findings will include observations present on the pelvic exam such as genital findings including location; presence or absence, and character of vaginal or cervical discharge or lesions; and results of any on site tests.
- 8. An additional unscheduled visit as deemed necessary by the site investigator to ensure short-term surveillance will be planned.
- 9. Participants will be reminded not to use tampons or any other vaginal products throughout the study.
- 10. Participants will be counselled to try to abstain from sexual intercourse for 12 hours after each study product application and 12 hours before the remaining study visits.
- 11. Participants will receive non-spermicidal lubricated condoms for their male sexual partners. Participants will be encouraged to use condoms if they engage in vaginal intercourse throughout the study.
- 12. An appointment for the next regular follow-up visit will be scheduled. Depending on the time of the enrolment and the average length of the participant's menstrual cycle, careful attention should be paid to the approximate time of the participant's next menstrual period when scheduling those visits. Later adjustments of those dates may be necessary.

Women with vaginal discharge or vaginitis symptoms at the unscheduled visit will be referred for standard treatment and continue to receive study product.

If the test results at the unscheduled visit suggest a urinary tract infection, cervicitis or vulvovaginitis, the participant will be referred for standard treatment and continue to receive study product.

If the clinician suspects the woman to have developed an STI since the last visit, appropriate tests will be conducted and if needed the woman will be referred to standard of care treatment in compliance with current CDC STI Treatment Guidelines. The participant should be treated in case of positive findings and continue to use study product.

Women who develop *symptomatic* BV confirmed by Nugent 7-10 on Gram stain at least 4 weeks after the last Metronidazole treatment will be retreated with Metronidazole. This practice follows CDC treatment guidelines and FDA recommendations. The 7-day course of Metronidazole will begin as soon as possible.

Women diagnosed with *asymptomatic* BV during the follow-up visit will not be retreated with Metronidazole.

If test results and clinical screening suggest a UTI, the woman will be managed as clinically indicated.

Participants who test HIV-positive after randomization, will discontinue study product, but continue follow-up and attend all remaining study visits to monitor for adverse events. HIV-specific care, including the provision of antiretroviral treatment and ongoing management will be

provided by the FRESH Study.

# 8.0 STUDY PROCEDURES/EVALUATIONS

# 8.1 Clinical Evaluations

The following assessments and procedures will be performed:

- Sociodemographic and participant contact information
- Medical, gynaecological and sexual history
- Review of concomitant medications
- Physical exam to include vital signs
- Pelvic exam
- Acceptability questionnaire

## 8.2 Laboratory Evaluations

8.2.1 Clinical Laboratory Evaluations

At the clinical site, the following tests will be performed using approved standard inhouse tests:

- Pregnancy will be tested by standard rapid urine βhCG assays.
- Urine will be tested by urine dipstick for evidence of urinary tract infection, with follow-up urinalysis (UA), if abnormal.
- HIV testing will be conducted using standardized algorithms.\*
- Cervical (or vaginal) swabs will be tested for *N. gonorrhoeae*, *T. vaginalis*, *Mycoplasma genitalium* and *C. trachomatis* by nucleic acid amplification.
- Gram-stained vaginal smear by Nugent's scoring system for diagnosis of BV
- 8.2.2 Special Assays or Procedures
  - Vaginal specimens will be analyzed for vaginal colonization with *L. crispatus* using qPCR assays and 16S rRNA gene/shotgun sequencing, which will be performed by a central laboratory at the Ragon Institute of MGH, MIT and Harvard
  - Cervicovaginal lavage (CVL) specimens will be analyzed for cytokines and chemokines using a luminex array
  - Cervical cytobrush samples will be used to assess presence of HIV target cells by flow cytometry.
  - Vaginal specimens will be analyzed using multiomic (e.g. proteomics, metabolomics, etc.) testing.
  - Vaginal samples will be used for culturing of live bacterial isolates for quenching and functional analysis
  - CVL will also be used for in vitro anti-HIV activity assays

# 8.2.3. Specimen Preparation, Handling, and Shipping

- Instructions for Specimen Preparation, Handling, and Storage will be described in further detail in the MOP.
- Many of the collected samples will be analyzed in laboratories in Durban and at UKZN.
- But some of your collected vaginal swabs will be shipped to a laboratory located in Boston, USA, headed by [name] of the Ragon Institute at MGH.
- Mucosal sampling swabs, and cytobrush cells will all be initially processed and stored at UKZN. Further analysis will be performed at both UKZN and in the U.S. at the Ragon Institute of MGH, MIT and Harvard. All work performed in the U.S. will be done in close collaboration with South African LACTIN-V investigators.
- Instructions for specimen shipment will be described in further detail in the MOP.

# 9.0 ASSESSMENT OF SAFETY

# 9.1 Specification of Safety Parameters

All AEs and SAEs will be collected through the Final Visit 19 (Day 64).

# 9.2 Methods and Timing for Assessing, Recording, and Analyzing Safety Parameters

#### 9.2.1 Adverse Events

ICH (International Conference on Harmonisation) E6 defines an AE as any untoward medical occurrence in a patient or clinical investigation subject administered a pharmaceutical product regardless of its causal relationship to the study treatment. An AE can therefore be any unfavorable and unintended sign (including an abnormal laboratory finding), symptom, or disease temporally associated with the use of medicinal (investigational) product. The occurrence of an AE may come to the attention of study personnel during study visits and interviews of a study participant presenting for medical care, or upon review by a study monitor.

All AEs including local and systemic reactions not meeting the criteria for "serious adverse events" should be captured on the appropriate CRF and will include:

- Vaginal bleeding other than menstruation
- Abnormal vaginal discharge
- Abnormal vaginal odor
- Genital itching
- Genital burning
- External genitalirritation
- External genital swelling
- Nausea
- Vomiting
- Abdominal pain/cramps
- Diarrhea
- Constipation
- Genital rash
- Pain/burning with urination
- Frequent urination
- Blood in urine
- Headache

Information to be collected includes event description, time of onset, clinician's assessment of severity, relationship to study product (assessed only by those with the training and authority to make a diagnosis), and time of resolution/stabilization of the event. All AEs occurring while on study must be documented appropriately regardless of relationship. All AEs will be followed to adequate resolution.

Any medical condition that is present at the time that the participant is screened should be considered as baseline and not reported as an AE. However, if it deteriorates at any time during the study, it should be recorded as an AE. All AEs must be graded for severity and relationship to study product. The FDA defines an AE as any untoward medical occurrence associated with the use of a drug in humans, whether or not considered drug related.

Severity of Event: All AEs will be assessed by the clinician using a protocol-defined grading system. For events not included in the protocol-defined grading system, the following guidelines will be used to quantify intensity.

- Mild (Grade 1): Events require minimal or no treatment and do not interfere with the participant's dailyactivities.
- Moderate (Grade 2): Events result in a low level of inconvenience or concern with the therapeutic measures. Moderate events may cause some interference with functioning.
- Severe (Grade 3): Events interrupt a participant's usual daily activity and may require systemic drug therapy or other treatment. Severe events are usually incapacitating.
- Life-threatening (Grade 4): Life-threatening consequences; urgent intervention indicated.

Changes in the severity of an AE should be documented to allow an assessment of the duration of the event at each level of intensity to be performed. AEs characterized as intermittent require documentation of onset and duration of each episode.

Relationship to Study Products: The clinician's assessment of an AE's relationship to test article is part of the documentation process, but it is not a factor in determining what is or is not reported in the study. If there is any doubt as to whether a clinical observation is an AE, the event should be reported. All AEs must have their relationship to study product assessed using the terms: related or not related. In a clinical trial, the study product must always be suspect. To help assess, the following guidelines are used.

- Related: There is a reasonable possibility that the study product caused the AE. Reasonable possibility means that there is evidence to suggest a causal relationship between the study product and the AE.
- Not Related: There is not a reasonable possibility that the administration of the study product caused the event.

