#### 2.6 Potential Risks and Benefits

#### 2.6.1 Potential Risks

#### 2.6.1.1 Biological Risks: LACTIN-V and Placebo

The study product contains a naturally occurring strain of *L. crispatus* CTV-05. To date, there has been considerable amount of experience using LACTIN-V at concentrations up to  $2 \times 10^9$  cfu/dose without any apparent related adverse effects, with the exception of a short duration of asymptomatic vaginal discharge. No serious adverse events have been reported in Protocol No. LV-001, LV-002 and LV-004 using LACTIN-V at 5 x 10^6 and 5 x 10^8 cfu/dose, and no subject left the protocol due to an adverse event. No severe or severe-related adverse event has been experienced by more than one subject. In Protocol No. LV-003, using LACTIN-V at 5 x 10^8 cfu/dose, one subject in the placebo group experienced three simultaneous SAEs unrelated to LACTIN-V. Two subjects in the LACTIN-V group discontinued study treatment due to AEs; one subject became pregnant and the other reported nausea and diarrhea, which required treatment.

Safety results of the recently completed Phase 2a trial (LV-006) assessed colonization efficiency, safety, tolerability and acceptability of LACTIN-V at 2 x 10^9 cfu/ dose in 24 women with BV. No Grade 3 AEs or SAEs were observed during the clinical phase of the study. Based on the DAIDS Toxicity Table Addendum for Vaginal Microbicide Studies (November 2007)  designed to standardize AE assessment, a total of 120 total AEs were reported, 108 (90%) of which were Grade 1 and 12 (10.0%) were Grade 2 severity. The most common genitourinary AEs included vaginal discharge of study product (46%), abdominal pain (46%) and dysuria (21%). AEs were evenly distributed between LACTIN-V and placebo groups. All enrolled women (n=24) reported at least one AE. A single participant receiving placebo discontinued herself from study product due to a moderate AE (vaginal irritation).

Risks from the administration of LACTIN-V are low since colonization with this type of organism is strongly associated with improved vaginal health. No systemic risks are anticipated since this is an organism that is applied topically and not expected to be absorbed. These risks will be explained in the written informed consent form. No pregnant women, fetuses, prisoners, children, persons with an active STI or women undergoing in vitro fertilization are included in this study.

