Coinciding with the regular twice weekly visits of the FRESH study, brief Check-in Visits will be conducted, during which directly observed product administration of the remaining doses will occur (Doses 4 - 11).

- a. Check-In Visit 4 (Day 11), Dose 4 (Dose 5 to take home for Day 12)
- b. Check-In Visit 5 (Day 15), Dose 6
- c. Check-In Visit 6 (Day 18), Dose 7
- d. Check-In Visit 7 (Day 22), Dose 8
- e. Check-In Visit 8 (Day 25), Dose 9
- f. Check-In Visit 9 (Day 29), Dose 10
- g. Check-In Visit 10 (Day 32), Dose 11

The following short assessments will be performed at these Check-In Visits 4 - 10:

- 1. Staff will review symptoms, concomitant medications, last menses, sexual activity and any medical problems since the last visit, which will be recorded on the appropriate CRF.
- 2. The participant will be asked to provide exact dates and times of those study product administrations that took place at home (Dose 2,3 and 5 only).
- 3. Staff will hand the appropriate dose (4, 6- 11) to the participant from the carton stored on site, labeled with the participant's study ID.
- 4. In Week 1 only, staff will hand the fifth dose to the participant from the carton on site, to take home and self-administer the next day (Day 12)
- 5. Staff will document the study product administration on the appropriate CRF.
- 6. Participants will be reminded not to use tampons or any other vaginal products throughout the study.
- 7. Participants will be encouraged to use the provided non-spermicidal condoms if they engage in vaginal intercourse throughout the study.
- 8. Participants will be counselled to try to abstain from sexual intercourse for 12 hours after each study product application and for 12 hours before those study visits that include a gynaecological exam.
- 9. An appointment for the next Check-In, Follow-Up or Final Visit will be confirmed or rescheduled if necessary. Depending on the time of the enrolment and the average length of the participant's menstrual cycle, careful attention should be paid to the approximate time of the participant's next menstrual period when scheduling those visits. Later adjustments of those dates may be necessary.

If the participant fails to cancel the appointment and reschedule, and she is unreachable during the agreed upon time for the telephone interview, the study team will make three attempts to reach the participant to reschedule the telephone interview.

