# 9.4 Type and Duration of Follow-up of Subjects after Adverse Events

AEs and SAEs will be followed from the time of study treatment through resolution even if this extends beyond the study-reporting period. Resolution of an AE/SAE is defined as the return to pretreatment status or stabilization of the condition with the expectation that it will remain chronic.

Follow-up procedures, evaluations, and outcomes will be recorded on the appropriate data collection form.

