Sparse clustering, where clustering and feature selection are integrated, will be used to identify study subjects with similar microbial profiles. Sparse clustering has a number of advantages. If the underlying groups differ only in terms of some of the features, then it might result in more accurate identification of these groups than standard clustering. It also yields interpretable results, since one can determine precisely which features are responsible for the observed differences between the groups or clusters. Similarly, Sparse Principal Component analysis will be used to group a set of highly correlated microbial reads to uncorrelated summary variables. As in Objective 1, adjustment for multiple testing will be made using less conservative multiple testing correction methods (e.g., Benjamini-Hochberg).

Solicited AEs will be analyzed by taking the most severe response over the Day 64 followup period. The analyses of AEs and SAEs is mainly descriptive. Descriptive measures (frequency and percent) will be used to summarize the proportion of participants with product-related AEs (Grade 0, Grade 1, Grade 2, and Grade 3) in each treatment arm. Confidence intervals for AEs rates will be estimated using methods for exact binomial confidence intervals. Fisher's exact test will be used to compare rates of AEs between the two treatment arms. Multivariate analyses using logistic regression models will be used to compare AEs rates between the two arms while adjusting for the effect of other covariates.

Unsolicited AEs will be coded by MedDRA® for preferred term and system organ class. The proportion of participants and exact 95% confidence intervals of AEs in aggregate, as well as by MedDRA® categories, will be computed. The number of SAEs will be reported by a detailed listing showing the type, MedDRA® coding, relevant dates (treatment dosing dates and AE onset and resolution dates), severity, relatedness, and outcome for each event.

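### The adverse-event baseline is tied to an undefined screening time rather than to Day 8 before dose 1, with no participant-reported symptom review scheduled on Day 8 and no onset-after-dose-1 condition in the arm comparison

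*Combined protocol and SAP*

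**What the plan says.** **Baseline.** Section 9.2.1 states: "Any medical condition that is present at the time that the participant is screened should be considered as baseline and not reported as an AE". The next sentence qualifies it: "However, if it deteriorates at any time during the study, it should be recorded as an AE". Neither sentence says which visit counts as screening, or against which visit deterioration is judged.

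**AE period.** Section 9.2.1 adds: "All AEs occurring while on study must be documented appropriately regardless of relationship". Section 9.1 gives an end to collection (Day 64) but no start. Section 9.4 uses a different starting point: "AEs and SAEs will be followed from the time of study treatment through resolution".

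**Collection.** The Visit 3 (Day 8) procedure list in section 7.3 has no symptom or AE item. The recurring review appears first in section 7.4, for the check-in visits that begin on Day 11: "Staff will review symptoms, concomitant medications, last menses, sexual activity and any medical problems since the last visit".

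**Analysis.** Section 11.5 states: "Solicited AEs will be analyzed by taking the most severe response over the Day 64 followup period". It summarises product-related AEs by grade and arm, and compares AE rates between arms with Fisher's exact test. That test is not restricted to related events or to events with onset after dose 1.

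**The concern.** Women enter with a Nugent score of 4 to 10, take metronidazole on Days 1 to 7 and receive the first randomised dose on Day 8. Their status before metronidazole is therefore not their status when randomised exposure begins. A safety comparison of LACTIN-V with placebo needs the second.

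Safety is part of primary Objective 3. Vaginal discharge is the one effect that section 2.6.1.1 lists as most likely, and several other solicited events in section 9.2.1 (odour, itching, burning) can also be present in a woman with disturbed flora before treatment. Symptoms that a live vaginal product might bring back are thus among those that a pre-metronidazole baseline can excuse. Separately, gastrointestinal symptoms or headache that begin on metronidazole are on-study events. Nothing in section 11.5 keeps them out of a worst-grade comparison meant to describe the randomised product.

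**Working it through.** No arithmetic settles this point, so the passages are set side by side. The only safety figure in the plan is the section 11.4 table for 60 participants. Using 1 - (1 - p)^60 at p = 0.5%, 1%, 2% and 5% gives 0.260, 0.453, 0.702 and 0.954, which matches the printed 0.26, 0.45, 0.70 and 0.95. It has no bearing on the baseline.

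**Step 1: order of events**

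| Time | What is scheduled | Source |
|---|---|---|
| FRESH Week 5, then Day 1 | Eligibility tests, history; metronidazole starts on Day 1 | 4.0, 7.1 |
| Day 4 | Metronidazole dosing; no AE review listed | 7.2 |
| Day 8 | Concomitant medications, pelvic examination, urine tests, findings to CRF (item 5), randomisation (item 7), dose 1 (item 8) | 7.3 |
| Days 9 and 10 | Doses 2 and 3 at home | 7.3 |
| Day 11 | First AE check; dose 4 | 4.0 timeline, 7.4 |

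In Appendix A the symptom-review and AE-assessment rows are also blank at Randomization and first marked at Visits 4-10. That table alone would be weak evidence: its AE-assessment row is also blank at the Final Visit, where section 7.7 does require AE assessment. But the section 7.3 list and the section 4.0 timeline agree with it for Day 8. The Day 11 review looks back only to the previous visit, which is Day 8.

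**Step 2: how the rule classifies a symptom**

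| At screening | Day 8 before dose 1 | On product | Current text | Day 8 baseline |
|---|---|---|---|---|
| Absent | Absent | Appears | AE | Product-phase AE |
| Present | Cleared | Returns, worse than at screening | AE (deterioration) | Product-phase AE |
| Present | Cleared | Returns, no worse than at screening | Can be treated as baseline | Product-phase AE |
| Absent | Began on metronidazole | Persists unchanged or resolves | AE; can enter the worst-grade comparison | Listed separately |

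Only the third and fourth rows change.

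**Step 3: what Day 8 does record.** Appendix A marks a medical, gynaecological and sexual history and a symptom-directed examination at Randomization. Section 7.3 item 5 puts observed discharge on the CRF before dose 1. For clinician-observed discharge there is therefore a pre-dose record. For odour, itching, burning, gastrointestinal symptoms and headache, which are mainly participant-reported, no solicited record is scheduled.

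**Step 4: direction of effect.** Let p_L and p_P be the true product-phase event probabilities in the LACTIN-V and placebo arms.

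- *Fourth row.* Let q be the probability of a recorded metronidazole-week event, equal in both arms in expectation because it precedes randomisation, and independent of later events. The counted rates are q + (1 - q)p_L and q + (1 - q)p_P. Their difference is (1 - q)(p_L - p_P).
- *Third row.* Let a share s have the symptom at screening, with the same later risk as the others and none of their returns counted. The rates become (1 - s)p_L and (1 - s)p_P. Their difference is (1 - s)(p_L - p_P).

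Under these assumptions either mechanism shrinks the difference and neither reverses it. The documents give neither s nor q, so no value is put in.

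**The case against.** The strongest reply is that the plan already contains most of what is needed.

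- **Deterioration is an AE.** This stands for new or worse symptoms. A clinician might also call a symptom that cleared and came back a deterioration, and section 9.2.1 says to report when in doubt. But the reference point for deterioration is not given, so return to the screening level is left to individual judgement. Appendix B grades participant-reported discharge against the woman's usual amount and her baseline, which does not supply a date either.
- **Day 8 is not unassessed.** This stands in part. Besides the history and examination, section 5.3.3.1 withdraws women at Visit 3 for symptomatic candidiasis, which presupposes asking about symptoms. What is missing is a scheduled, solicited symptom and AE record.
- **Screening may extend to Day 8.** Section 7.3 calls women excluded on Day 8 screening failures, so this reading is possible. It shows that the term is ambiguous; it does not settle it.
- **Onset time and relatedness are collected.** This stands for recorded events: onset dates can separate those that began before dose 1. They cannot recover a symptom never recorded because it was called baseline.
- **The Objective 3 outcome is product-related AEs, and the AE analysis is mainly descriptive.** This largely stands. An event before any randomised product should not be judged related to it. One loose end is that section 6 describes metronidazole under the study-product heading.

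A reader might go further and infer that product-emergent discharge will generally be dismissed, or that metronidazole effects bias the comparison against one arm. The documents support neither. Worse discharge is reportable, observed discharge is recorded on Day 8, and metronidazole is given to everyone before randomisation. Nor would metronidazole-week events be fully captured, since no visit that week is scheduled to solicit them; only those that happen to be recorded can dilute the comparison.

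**Conclusion.** The point holds in a limited form. On the ordinary reading of screening as preceding metronidazole, the plan permits one class of product-phase symptom to go unrecorded: present at screening, cleared by Day 8, returning at no more than the screening level. Day 8 data only partly make up for it, and an unsolicited Day 8 symptom status cannot be reconstructed later. Separately, the all-AE Fisher comparison can include recorded metronidazole-week events. That dilutes the contrast in both arms alike and does not favour one arm; the product-related summary is largely unaffected.

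No numerical size should be attached. The documents give no screening symptom prevalence and no metronidazole-week event rate. A reader might be tempted to use the 46% for discharge of study product in section 2.6.1.1. That figure covers a 24-woman trial without an arm split, in which AEs are described as evenly distributed between groups, so it yields no arm difference to shrink. Nor is it shown to be the same condition as discharge present at screening.

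The change is worth making because it is cheap and because under-recording and dilution both push a small safety comparison (20 against 40 women) towards showing no difference.

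**What to change.** 1. **Section 9.2.1:** define the baseline for randomised-product AEs as the woman's status on Day 8 immediately before dose 1, and judge worsening against that status.
2. **Section 7.3 and Appendix A:** add the existing symptom and AE review to Visit 3, placed before dosing and covering the solicited list in section 9.2.1.
3. **Section 11.5:** limit the between-arm AE comparison, including the worst solicited grade, to events that start or worsen after dose 1 relative to Day 8. List events from Day 1 up to dose 1 on Day 8 separately, so that they remain documented without entering the randomised contrast.

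The cost is one existing CRF page at an existing visit, plus short wording changes in the sections named. Recorded symptom rates may rise slightly, because returning symptoms that could have been called baseline will be counted.
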